Study title: Effects of virtual reality on cardiorespiratory fitness test results

IRB approval number: 2130870

Document date: 2/21/2024

Protocol Title:

Effects of virtual reality on cardiorespiratory fitness test results

Participants

A power analysis using G*Power version 3.1 will be conducted to determine sample size adequacy. We anticipate a moderate-large effect ($d = 0.7$) of VR on physiological outcomes based on past studies using similar designs (Rutkowski et al., 2021). With an alpha level of .05 and a power level of .80, an estimated 19 participants will be needed to observe a significant effect on $\dot{V}O_{2\text{peak}}$.

To account for participant dropout and missing data, we will recruit an additional 5 participants for a total of 24 participants. The primary means of participant recruitment will be the posting of approved informational flyers throughout the Forrest Hills, Summerville, and Health Science campuses of Augusta University. A secondary means of recruitment will be word-of-mouth. Approved study fliers will also be shared with other instructors at the affiliated institution so that they may announce the study opportunity to their students and share the flier on learning management systems.

Healthy men and (non-pregnant) women 18 years and older will be recruited to take part in this study. Prospective participants will be operationally defined as “healthy” according to results of the 7-item Physical Activity Readiness Questionnaire [PAR-Q; Warburton et al. (2019)]. Answering “yes” to any of the risk assessment questions will result in exclusion from study participation.

Research design

A repeated-measures crossover design will be used in which healthy participants complete a familiarization session and two experimental trials. Experimental days consisted of a maximal graded exercise test with (VR) and without (Control) the use of the immersive VR program separated by at least 1 week. The order of the conditions on the experimental trial days will be counterbalanced and randomized. Cardiometabolic data and psychological responses will be collected during the exercise tests to address the aims of the study. This study will be approved by the associated Institutional Review Board (project 2130870). Written informed consent for each participant will be obtained prior to their participation.

Instruments

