The procedures for the two experimental session visits will be the same, aside from the use of the VR equipment in one of the visits. The order of the visits (control and VR) will be counterbalanced and randomized prior to the study commencement. Upon arrival to the lab, participants verbally confirmed that they had abstained from alcohol and strenuous exercise for the previous 24 hours and attained at least 6 hours of sleep the night prior to the visit. They will don the HR monitor, review the psychological scales, and adjust the exercise bike as needed. The gas collection apparatus will be donned and the collection tube will be connected from the mouthpiece to a metabolic cart that has been previously calibrated to the manufacturer specifications. The participant will sit on the exercise bike seat and, once ready, pedal against no resistance for 3 minutes as a warm-up. The exercise test will begin after the warm-up by increasing the resistance to 50 W and increasing the work rate by 25 W each minute thereafter until the termination of the exercise test (Bird et al., 2019). RPE and affective valence responses will be collected at the end of every odd numbered minute (end of minutes 1, 3, 5, etc.). Heart rate will be collected continuously and monitored throughout the test. See Figure 1 for visual timeline of data collection.

The test will be terminated upon volitional exhaustion (when the participant feels that they can no longer continue), when the participant fails to maintain cadence > 50 rpm for longer than 10 s, or when a plateau in $\dot{V}O_2$ (<100 ml/min increase with an increase in work rate) is observed (Poole, Wilkerson, & Jones, 2008). A cool-down period of 3 min at 0 W (no resistance) will immediately follow the termination of the exercise test. At the end of the cool-down, participants will complete the remembered pleasure scale. This will mark the end of the visit and the participant will be directed from the lab.

The experimental session visit which for which the VR equipment is used will be identical in all ways to the control condition, with the exception that the VR headset will be worn in addition to the other previously mentioned equipment. A video displaying natural scenery from the viewpoint of a cyclist will be viewed by the participant throughout the exercise test. Once both experimental visits have concluded, the participants' participation in the study is complete.

Figure 1. Data collection timeline during exercise tests

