	Stage of Exercise Test											Cool down	
	Warm-up	1	2	3	4	5	6	7	8	9	10		
Work Rate (W)	0	50	75	100	125	150	175	200	225	250	275	...	0
Duration (min)	3	1	1	1	1	1	1	1	1	1	1	1	3
HR	X	X	X	X	X	X	X	X	X	X	X	X	X
Metabolic data	X	X	X	X	X	X	X	X	X	X	X	X	X
Affective Valence	X	X		X		X		X		X		X	
RPE	X	X		X		X		X		X		X	

"X" = measurement taken at this time point

Procedures for risk management

- **Risk of musculoskeletal injury** – The probability of risk will be reduced primarily by excluding high-risk individuals from participation in the study via the PAR-Q screening questionnaire. Participants will also have a sufficient warm-up time built in to the exercise test to minimize the risk of muscle injury. The gradual increase in work rate over the course of the test will also ensure that physiological demands are reasonable and that risk of muscle injury is limited.
- **Risk of lightheadedness and loss of balance** – the research team members will be standing adjacent to the participant during the exercise test on either side of the equipment to prevent the participant from falling off of the bike in the event of excessive fatigue and shortness of breath during and following the exercise. The investigator will also emphasize that the participant is able to terminate the test at any time for any reason, including severe shortness of breath or lightheadedness, simply by ceasing to pedal on the bike. A sufficient cool down period (3 minutes of cycling at no resistance) will be used to prevent blood from pooling in the veins of the lower body and ensure that blood circulation to the brain and the rest of the body continues after the exercise test has ended.
- **Dehydration** – an unopened bottle of drinking water will be made available to the participant at the start of the study. The participant will be allowed to drink *ad libitum* before and after the exercise test. Drinking water during the test is not possible when the facemask is being worn for data collection purposes.
- **Muscle soreness** – some muscle soreness after a maximal exercise test is unavoidable, but the discomfort participants might encounter will be reduced by ensuring participants have a cool down period after the test.

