Study title: Effects of virtual reality on cardiorespiratory fitness test results

IRB approval number: 2130870

Document date: 6/7/2024

Statistical Analysis Plan

Analysis of data will be completed with SPSS version 29, applying an alpha level of .05. All data will be screened for data entry errors, outliers (difference scores >3.29 standard deviation units from the mean difference score between the two conditions), normality, and homogeneity of variance before formal analysis.

The primary outcome variables $\dot{V}O_{2\text{peak}}$ and workload at ventilatory threshold will be compared between conditions (Control and VR) using separate one-way repeated-measures ANCOVAs (analysis of covariance), with preference for exercise intensity subscale of the PRETIE-Q (Ekkekakis et al., 2005) as the covariate.

The secondary outcome measures of peak power, total test time, % $\dot{V}O_{2\text{peak}}$ at ventilatory threshold, heart rate (HR) at $\dot{V}O_{2\text{peak}}$, HR at ventilatory threshold, respiratory exchange ratio (RER) at $\dot{V}O_{2\text{peak}}$, and RER at ventilatory threshold will similarly be compared between conditions using a series of repeated-measures ANCOVAs with preference for exercise intensity subscale of the PRETIE-Q as the covariate.

Rating of perceived exertion (RPE) and affective valence will be analyzed with separate linear mixed-effects model analyses. Individual participants will be specified as the correlated random effect. The fixed factors will be timepoint and condition.

Results of ANCOVAs will be accompanied by partial eta squared (η^2) as a measure of effect size (small = 0.01; medium = 0.06; large = 0.14). Linear mixed-effect analysis results will use Cohen's d as a measure of effect size (small = 0.20; medium = 0.50; large = 0.80).

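### The mixed model for RPE and affective valence has participant as its only random effect, so the VR-versus-Control test uses the wrong error term and its type I error can lie above or below .05

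*SAP*

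**What the plan says.** The fourth paragraph of the SAP assigns RPE and affective valence to separate linear mixed models and describes their structure in two sentences: "Individual participants will be specified as the correlated random effect. The fixed factors will be timepoint and condition". It names no visit-level term, random slope, residual covariance or degrees-of-freedom method, and does not say whether a condition-by-timepoint interaction is fitted. The protocol gives no model for these outcomes. The general test level is in the SAP's first paragraph: "Analysis of data will be completed with SPSS version 29, applying an alpha level of .05".

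The protocol fixes the data structure:

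- Under Research design, each participant has one maximal test "with (VR) and without (Control) the use of the immersive VR program separated by at least 1 week".
- Under Visits 2 and 3, "RPE and affective valence responses will be collected at the end of every odd numbered minute". Figure 1 marks 5 such ratings over its 10 numbered stages, or 6 with the warm-up.
- Everyone follows the same absolute protocol, "increasing the resistance to 50 W and increasing the work rate by 25 W each minute thereafter".

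**The concern.** Condition is a visit-level factor, so each participant supplies one VR-minus-Control contrast however many ratings are taken within a visit. A participant intercept alone treats all ratings from a person as independent once timepoint and condition are accounted for. Two sources of variation outside that model affect the condition test in opposite ways.

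- **Visit-level shifts and serial correlation.** If a participant rates higher throughout one visit, or successive ratings in a visit resemble each other, the VR contrast is noisier than the pooled residual implies. The test is then liberal.
- **Participant-by-timepoint differences.** Common absolute work rates are relatively harder for less fit participants, so stable individual differences in the rating curve are plausible. They cancel from VR minus Control but stay in the pooled residual. The test is then conservative.

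At stake are the p-value and interval for the VR effect on these two outcomes: a false finding in one case, a missed effect in the other.

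**Working it through.** **The plan's own figure.** The protocol states: "With an alpha level of .05 and a power level of .80, an estimated 19 participants will be needed". A two-sided paired t-test with d = 0.7 taken as the standardised mean difference gives n = 19 with power 0.823, so the figure reproduces. It concerns VO2peak and is untouched by this point. For RPE and affective valence the documents give only the alpha level.

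**Inputs.** n = 19 and alpha = .05 come from the documents; T = 5 ratings per visit comes from Figure 1 without the warm-up. Residual variance is set to 1. Two ratios are assumed, because the documents give none:

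- v = participant-by-visit variance / residual variance, 0 to 1
- w = participant-by-timepoint variance / residual variance, 0 to 2

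**Degrees of freedom.** There are 19 × 2 × 5 = 190 ratings. With main effects of timepoint and condition only, the pooled residual has 190 − 1 − 18 − 4 − 1 = 166 df: 18 for participant-by-condition, 72 for participant-by-timepoint, 72 for the three-way term and 4 for condition-by-timepoint. With the interaction fitted it has 162.

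**Expected mean squares with no VR effect.**

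- Condition: 1 + 5v
- Participant-by-condition: 1 + 5v (18 df), the matching error term
- Pooled residual: 1 + (18·5v + 72·2w)/166

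**True standard error divided by the model's** = √[(1 + 5v) / (1 + (90v + 144w)/166)]:

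- v = 0.1, w = 0: √(1.5/1.054) = 1.19
- v = 1, w = 0: √(6/1.542) = 1.97
- v = 0.1, w = 1: √(1.5/1.922) = 0.88
- v = 0, w = 2: √(1/2.735) = 0.60

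**Break-even.** The two mean squares agree when 166·5v = 90v + 144w, that is 740v = 144w, so w = 5.14v. The test is liberal below that line and conservative above it.

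**Type I error at nominal .05** (balanced simulation, 40,000 replicates per cell, 166 df):

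| v | w = 0 | w = 0.5 | w = 1 | w = 2 |
|---|---|---|---|---|
| 0 | .051 | .018 | .008 | .001 |
| 0.1 | .101 | .052 | .026 | .008 |
| 0.25 | .160 | .100 | .064 | .029 |
| 0.5 | .234 | .169 | .124 | .071 |
| 1.0 | .320 | .259 | .215 | .150 |

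Drawing the mean squares directly from their chi-square distributions agrees with every cell to within about .003.

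**Variations.**

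- Serial correlation alone (AR(1), v = w = 0): .136 at correlation .3, .219 at .5.
- n = 24, w = 0: .097 to .315 for v = 0.1 to 1.0.
- Seven ratings per visit, n = 19, w = 0: .123 at v = 0.1 and .392 at v = 1.0.
- Unequal test lengths (3 to 7 ratings per visit, REML random-intercept fits, 2,000 per cell), w = 0: .048, .092, .173 and .333 at v = 0, 0.1, 0.25 and 1.0. At v = 0.1, w = 1: .035.

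**Matching error term.** Testing condition against participant-by-condition variation on 18 df gave .048 to .052 in every n = 19, 5-rating scenario. In the unequal-length cells, a paired test of mean differences gave .049 to .058.

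**The case against.** The strongest reply is that the SAP gives a short description, not full syntax. The word *correlated* is unexplained and may stand for a random condition slope or a visit-level covariance, in which case the problem shrinks. That is possible, but no such term is written. If one is intended, the SAP must say so.

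Second, every variance ratio here is assumed, the two sources can offset each other (.052 at v = 0.1, w = 0.5), and the choice of grid shapes the picture. At v = 0.5 and v = 1 break-even needs w of 2.6 and 5.1, beyond the grid's limit of 2, so those rows cannot show a conservative result. This stands: the table shows what can happen, not what will, and counting its cells says nothing about the likely direction.

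Third, the visits are standardised: Visits 2 and 3 set rules on alcohol, strenuous exercise and sleep and include a review of the scales. These may reduce visit shifts, but nothing shows they remove them, and v = 0.1 alone doubles the error. Nor do they address participant-by-timepoint differences.

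Fourth, 166 df assumes main effects only. That is so, but fitting the interaction (162 df) moves no cell by more than about .004.

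Finally, neither outcome is on the SAP's primary or secondary list. That limits the weight of the point. Even so, Research design ties psychological responses to the study aims, and the SAP gives them their own analysis.

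**Conclusion.** The concern holds. As written, the model tests a visit-level factor against within-visit noise. Its p-value and interval for VR on RPE and affective valence are correctly calibrated only if visit-level variation, serial correlation and participant-by-timepoint variation are all absent or happen to offset. In the assumed scenarios the true standard error is 0.60 to 1.97 times the model's. The documents do not determine the direction. The conclusion rests on the literal reading of participant as the only random effect; the sizes rest on the assumed ratios and, for the main table, on complete balanced data. The scope is these two outcomes only. It should be corrected before analysis.

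**What to change.** State the structure in the SAP: random effects for participant, for visit within participant (participant-by-condition) and for participant-by-timepoint, or a within-visit residual covariance, as far as estimable, with Satterthwaite or Kenward-Roger degrees of freedom. State also whether the condition-by-timepoint interaction is fitted and whether the warm-up rating is included.

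A visit term alone is not enough. It removes the inflation, but with variances bounded at zero the type I error stays at .025 at v = 0.1, w = 1, because the visit variance is estimated as zero in 81% of runs. With both terms it is .048 there, and .037 to .052 over the whole grid. The fuller model is therefore slightly conservative when visit variance is zero.

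Prespecify a fallback for non-convergence: a paired test of each participant's mean VR-minus-Control difference over timepoints reached in both visits. Because VR may itself change test time, which is a secondary outcome, the SAP should say that this comparison covers only the shared part of the two tests.

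The cost is one or two extra random terms in the SPSS MIXED syntax, one SAP sentence, and fewer error degrees of freedom for condition (18 instead of 166 at n = 19). P-values may move either way.

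### With 19 to 24 participants analysed, the SAP's partial eta squared cut-offs call every significant ANCOVA condition effect 'large', and no VR minus Control difference or confidence interval is named

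*SAP*

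**What the plan says.** The final paragraph of the SAP states: "Results of ANCOVAs will be accompanied by partial eta squared", given "as a measure of effect size (small = 0.01; medium = 0.06; large = 0.14"). This covers the two primary outcomes (VO2peak and workload at ventilatory threshold) and the seven secondary outcomes. The secondary outcomes are analysed by "repeated-measures ANCOVAs with preference for exercise intensity subscale of the PRETIE-Q as the covariate", and the primary outcomes use the same covariate. The opening paragraph sets the test level, "applying an alpha level of .05".

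The protocol's Participants section gives the sample size: "an estimated 19 participants will be needed to observe a significant effect on" VO2peak, and then "we will recruit an additional 5 participants for a total of 24 participants".

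Neither document names a VR minus Control difference in native units, a confidence interval or a smallest difference of interest for any ANCOVA outcome. A mean difference score appears only in the SAP's outlier-screening rule. RPE and affective valence go to mixed models with Cohen's d and are outside this point.

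**The concern.** A three-level size scale is useful if it separates effects that matter from effects that do not. For a two-condition within-person contrast, partial eta squared depends only on F and the error degrees of freedom, so at a given n it maps one-to-one onto p. If the significance threshold lies above the 'large' cut-off, then 'small' and 'medium' can never attach to a significant result, and 'large' adds nothing to p < .05. Just below the threshold, a result that does not exclude zero is also called 'large'.

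The study asks whether and how far VR shifts fitness test results. Partial eta squared has no sign and no units, so it shows neither the direction of a VO2peak shift nor its size. Those come from the paired difference and its interval, which the plan does not commit to report.

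**Working it through.** **Inputs.** Alpha .05 (SAP, opening paragraph; Protocol, Participants). n from 19 to 24 and d = 0.7 (Protocol, Participants). Two conditions, so 1 numerator df, and one between-person covariate, so error df = n − 2 (SAP). Cut-offs .01, .06 and .14 (SAP, final paragraph). Sidedness is not stated, and d is taken as a paired dz.

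**The plan's own figure.** For a two-sided paired t test with d = 0.7 and alpha .05, exact noncentral-t power is 0.823 at n = 19, the smallest n that reaches .80. One-sided testing would give 15. The stated 19 therefore reproduces as a two-sided paired test. Power at n = 24 is 0.907.

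**Smallest significant partial eta squared** = Fcrit / (Fcrit + error df):

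- n = 19: 4.451 / (4.451 + 17) = .2075
- n = 24: 4.301 / (4.301 + 22) = .1635
- n = 28: 4.225 / (4.225 + 26) = .1398, the first n below .14 and above the 24 recruited

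The values for n = 20 to 23 are .197, .187, .179 and .171. With no df spent on the covariate (error df = n − 1), the end points are .197 and .157, and the conclusion is the same.

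**p-value at the 'large' cut-off.** F = .14 × error df / .86:

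- n = 19: F = 2.767, p = .1145
- n = 24: F = 3.581, p = .0717

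As a paired effect, √(F/n), this is about 0.38 (n = 19) to 0.39 (n = 24). At the 'medium' cut-off of .06, p = .31 (n = 19) or .25 (n = 24), so the labels do still separate the smaller non-significant results.

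**How often 'large' falls on a non-significant result.** This is P(partial eta squared ≥ .14) − P(p < .05). For a non-zero effect it uses the noncentral F with ncp = n × dz², for the condition effect at mean preference.

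| True dz | n | P('large') | P(p < .05) | 'Large', not significant | Share of 'large' labels |
|---|---|---|---|---|---|
| 0 | 19 | .1145 | .050 | 6.5% | 56% |
| 0 | 24 | .0717 | .050 | 2.2% | 30% |
| 0.2 | 19 | .238 | .131 | 10.7% | 45% |
| 0.2 | 24 | .199 | .155 | 4.3% | 22% |
| 0.7 | 19 | .913 | .820 | 9.3% | 10% |
| 0.7 | 24 | .933 | .906 | 2.7% | 3% |

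Over nine ANCOVAs under the null, the expected count is 9 × .0645 = 0.58 (n = 19) or 9 × .0217 = 0.19 (n = 24). An expected count does not need the outcomes to be independent.

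**Centring, a separate matter.** The SAP does not say whether the preference score is centred or whether the model has a condition-by-preference term. If that term is fitted to an uncentred score, the condition effect is the effect at preference = 0. Its SE is √(1 + n r² / (n − 1)) times the centred SE, where r is the mean/SD of the score. The documents do not give r. Assuming 2 to 4, the factor is √(1 + 19 × 4 / 18) = 2.3 to √(1 + 19 × 16 / 18) = 4.2 at n = 19; n = 24 gives the same to one decimal. The thresholds above do not depend on this.

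**The case against.** The strongest reply is that the SAP promises a number, with benchmarks in brackets, and does not say that results will be reported by label alone. That stands. Among significant results at n = 19, partial eta squared runs from .2075 upward (.33 at p = .01, .48 at p = .001); at n = 24 it runs from .1635 (.27 and .40). A reader might infer that the effect-size reporting carries no information about significant results. The documents do not support that: only the word 'large' is uninformative.

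The benchmarks are conventional, and any standardised effect for a two-condition paired contrast is tied to F at a fixed n. That is also true. The point is narrower: at this n, the stated scale has one reachable level for a significant effect.

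A reader might also take the 56% and 30% shares as the general rate of misleading labels. They hold only if VR has no effect. At the effect the protocol plans for, they fall to 10% and 3%. The misreading also requires the reader to overlook the p-value beside the label.

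Finally, condition means may well be published anyway. But condition means and SDs alone do not give the precision of a paired difference, which also needs the within-person correlation, and the plan does not commit to the difference or its interval.

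**Conclusion.** The point holds as a weakness of reporting and interpretation, limited to the nine ANCOVAs. For any n from 19 to 24 at alpha .05, a significant condition effect is always 'large', and a non-significant one is also 'large' for p from .05 up to .1145 (n = 19) or .0717 (n = 24). This rests only on n, alpha and the error df, not on any SD or on centring. Fewer participants analysed or a stricter alpha would raise the threshold further. The frequencies at dz = 0.7 rest on reading the protocol's d as a paired effect.

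A reader might infer a fault in the tests or the sample size. There is none here: the stated 19 reproduces, and the cut-offs decide no test. The centring question is different, because it can change F and p, but it arises only if a condition-by-preference term is fitted. The 2.3 to 4.2 inflation rests on an assumed mean/SD ratio.

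**What to change.** In the SAP's final paragraph, drop the small/medium/large labels for the ANCOVAs and add, for example: 'For each ANCOVA outcome we will report the VR minus Control mean difference in native units with its 95% CI. Partial eta squared will be given as an unlabelled supplement.'

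Separately, state whether the model contains a condition-by-preference term. If it does, add: 'The preference score will be centred at the mean of the participants analysed for that outcome.' The difference, CI, F and p then all refer to the effect at mean preference.

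The first change costs only wording and slightly more reporting, and some effects lose a 'large' label. Alpha, sample size and model family stay as they are. The second can change F and p, including for both primary outcomes, so it must be fixed before the data are analysed.
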